## 9.4 Interim Analyses and Stopping Rules

The study will include an interim analyses after 30 and 45 subjects have completed enrollment. The Hyabittle-Peto method will be used determine whether the study should be stopped due to extreme differences between the active and control groups. At either interim analysis if the p-value for the primary efficacy outcome is <0.0013 the study will be determined to have met the endpoint.

In the event of a serious adverse event related to the device/treatment the study will be halted until the safety issue can be addressed (see 7). Due to the small enrollment size, a pre-specified number of adverse events will not be used to trigger an interim analysis or early end to the study.

### 9.5 Data Analyses

Analysis of the **primary efficacy endpoint** will proceed as follows. Each adherent subject's Daily Log will be used to determine the average number of SUI episodes per day for the baseline and  $12^{th}$  weeks (see 5.5 regarding subject adherence). To accommodate the likelihood that some subjects will omit log data, the "weeks" referred to in the baseline and 12th week assessments refer to the first and last 5 entries in the Daily Log. The percent reduction in SUI episodes is then calculated by subtracting the final week average from the baseline average, dividing the difference by the baseline average, and multiplying by 100. Subjects with a percent reduction of  $\geq$ 50% are considered responders. The number of responders from each group is then compared using a one-tailed Fisher's exact test for groups of unequal size, and p $\leq$ 0.025. For example, if 24 of 40 subjects (60%) from the active group responded and 5 of 20 (25%) from the control group responded, the active treatment would be considered effective (p=0.01).

SUI episodes per day data can additionally be characterized simply in terms of percent reduction (independent of whether it reaches a 50% level of clinical significance) and the treatment groups analyzed using a 2 sample t-test with unequal group sizes. This approach is commonly reported in the literature. This value may additionally be reported but is not intended for use in determining whether the study met its endpoint. This use of a secondary analysis method on a single endpoint after success of the primary analysis method is generally understood to not inflate the Type 1 error rate, so no multiplicity adjustments are necessary.

Also note that confidence intervals and associated effect size calculations may also be made on the same data, but no multiplicity adjustments are warranted. Similarly, the data may be additionally analyzed using intent-to-treat criteria instead of with per-protocol criteria as defined in 5.5.

Regarding **secondary outcome measures**, three tests are prospectively defined with the intent of using the results to support future product labeling and marketing. The Hochberg procedure

with a total alpha of 0.05 will be used to address multiple endpoint related multiplicity problems. These secondary outcome measures are only intended to be analyzed if the primary efficacy endpoint is met. Accordingly, no Type 1 error rate multiplicity adjustment is retrospectively applied to the primary endpoint. The three test are:

- **24h Pad Weight** Subjects with pad weight reductions of ≥50% (i.e. clinically significant) will be considered responders and the groups will be compared using the Fisher's exact test in a similar manner to the analysis of the primary outcome measure.
- **I-QoL** Quality of life scores will be analyzed with respect to a change from baseline. Responders will be those with an I-QoL score increase of 2.5 points, which is defined in the FDA guidance as clinically significant. Treatment and control groups will be compared using the Fisher's exact test.
- **Pad Use** As with the 24h pad weight test, reduction in pad usage will be assessed with respect to a reduction in the number of pads used per day and a 50% reduction will be considered clinically significant. Subjects who do not use a pad during the baseline week will be excluded from the analysis.

Other analyses that may be made but which are not prospectively included within the group of three formal secondary outcome measures (and therefore are not considered with respect to multiplicity adjustments) include:

- Alternate analysis methods for the 24h Pad Weight, I-QoL and Pad Use test will be performed. For each, the mass/score/number data can analyzed using a paired sample ttest to determine whether there is a mean difference between the groups. Further, for the 24h Pad Weight test, a "cure" rate may also be calculated wherein a cure is defined in terms of dryness, which the FDA guidance document recommends defining as a pad weight increase of less than 1.3 grams.
- Usability surveys will solicit subject feedback pertaining to their experience with the product. Appropriate statistical methods will be used in reporting these subjective measures. For example, the Fisher's exact test may be used to determine whether a significant difference exists in responses to the question "Are you satisfied with the treatment"

In addition to characterizing outcome measures as achieving a clinically meaningful response (e.g. ≥50% change) or as change scores (i.e. delta values), post hoc analyses may investigate outcome measures using analysis of covariance (ANCOVA), wherein baseline values are modeled as covariates, which has the advantage of accounting for variation in the magnitude of the baseline. Additional post hoc ANCOVA may be performed with covariates including age, type of incontinence, BMI or other potentially relevant variables.

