## 4. SELECTION AND ENROLLMENT OF PARTICIPANTS

#### 4.1 Inclusion Criteria

All subjects must meet the inclusion criteria below to participate in this study. Any waiver of these inclusion criteria (or the subsequent exclusion criteria) must be approved by the Clinical Director on a case-by-case basis prior to enrolling the subject, and documented in the subject's Case Report Form (TR-1131-FORM-10).

- Predominant stress urinary incontinence as determined by responses to a series of three standard questions from the King's Health Questionnaire; specifically:
  - An affirmative response to "Do you lose urine with physical activities such as coughing, sneezing, running?",

- An affirmative or negative response to "Is it very difficult to control when you have a strong urge to urinate?",
- And, if an affirmative response to the second question, a negative response to "Are more of your incontinence episodes due to a strong urge to urinate than to abdominal pressure such as sneezing?"
- Mild-moderate incontinence symptoms as determined by self-reported typical number of accidents of 1 per 24 hours or more. Symptom severity is later verified with data from the Daily Log (See 5.4)
- Age: 21-75y
- Gender: Female

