- **Pre-Study Incontinence History and Usability Questionnaire** (Pre-study) Included in the pre-study activity is a questionnaire that investigates each subject's medical history as it pertains to incontinence as well as their perceptions and preferences regarding incontinence treatments (TR-1131-FORM-1). Some of this information may be utilized in post hoc subgroup analysis (see 9.5). It may also be useful in informing strategies for Elidah to effectively reach potential patients.
- Daily Log (Baseline week and treatment weeks) Subjects are required to maintain a Daily Log throughout the study (i.e. baseline week through 12th week). Among other items they log their treatment completion (Y/N), treatment intensity (0-35), number of incontinence episodes, and number of pads used (TR-1131-FORM-3). The log also provides space for the subject to add notes that may be relevant to subsequent analysis. The log is maintained by the patient in hardcopy and returned to Elidah at the end of the study for analysis (see 10.4). Alternatively, an equivalent electronic form may be utilized. The stress urinary incontinence episodes per day data will serve as the primary outcome measure (see 9.5). See 9.5 regarding handling of missing information, particularly as it relates to the weeks between the baseline and 12th week.
- **Post-Study Usability Questionnaire** (Post-study) At the end of the study subjects are asked for feedback regarding any perceived improvement in continence, their satisfaction with the treatment, the ease of use, and other issues that may inform opportunities for future device/treatment improvements (TR-1131-FORM-4).
- Adverse Events (Throughout Study) See 7.3.

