## 5.4 **Protocol Schedule**

The study comprises five stages: Pre-study, Baseline, Verification, Treatment, and Post-Study.

- **Pre-Study** –The subjects initiate pre-study activity, which includes completion of the I-QoL Questionnaire, the Pre-study Incontinence History and Usability Questionnaire, and the 24-hour pad weight test. The subject mails the pre-study materials back to Elidah. There is no difference in requirements between the two study arms.
- **Baseline** –Concurrently, the subjects maintain the Daily Log for 7 days to establish a baseline of the episodes/day and pads/day measures. No treatment is administered during this period. After 7 days the subjects submit the data to Elidah (electronically or hardcopy). Subjects are instructed that they should not perform baseline activity during menses or if they are ill. Note that it is acceptable to complete or return the pre-study materials throughout this 7 day baseline period. There is no difference in requirements between the two study arms.
- **Verification** If the 7 day baseline shows that the subject does not qualify based on urinary stress incontinence episodes, then the subject will be disqualified and the device will not be sent.
- Treatment Subjects will self-administer treatment with the Elitone device or a sham device according to their group assignment. The prescribed number of treatments starts at 5x/week and is reduced at points throughout the 12-week study duration. See Section 6 and Table 5-1 for a detailed description of the device and the treatment schedule. If subjects are ill or in menses during the twelfth study week they are instructed to extend treatment for at least 5 days after menses and/or they are in good health.
- Post-Study Upon completion of treatment subjects complete the post-study requirements, which include the I-QoL questionnaire, a 24-hour pad weight test, and a post-study usability

questionnaire. Subjects are requested to complete the requirements and return the study materials to Elidah within 3 days of completing treatment. There is no difference in post-study requirements between the two study arms.

 
Data used in primary and secondary endpoint analysis
 
Used to establish compliance.
 
	I-QoL Questionnaire	24-Hour Pad Weight Test	Pre-Study Usability Questionnaire	Number of Self- administered Treatment	Daily Log	Post-Study Usability Questionnaire	Adverse Events			
Pre-Study Data	•	•	•							
Baseline (Week 0)				0	•					

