## 9. STATISTICAL CONSIDERATIONS

#### 9.1 Sample Size and Power Analysis

The study is designed to test the null hypothesis that the treatment group and control group are not different (see 2.3). Specific reference is made to the number of subjects who achieve a  $\geq$ 50% reduction in stress urinary incontinence episodes per day when comparing the final outcome to a baseline measure. Several comparable studies were identified in the literature in which similar " $\geq$ 50% reduction in episodes" metrics were reported. From these, sample-size calculations were performed to provide confidence that sufficient subjects would be enrolled to protect against Type II error. Each of these calculations target 80% power and assume an alpha of 2.5%, a 2:1 treatment to control randomization ratio, and a single-tailed test.

• From Sand *et al*, 48% of subjects in the active group (2 treatments per day) were responders compared to 13% of subjects in a control (sham) group. Using these values in a chi-squared sample size calculation one finds that the treatment group for the proposed study needs to enroll 31 subjects.

<sup>1 Sand et al, "Pelvic floor electrical stimulation in the treatment of genuine stress incontinence: A multi-center, placebocontrolled trial", Am J Obstet Cycecol, 173(1):72-79, July 1995.

- From Richardson *et al*, 62% and 73% of subjects (1 treatment/day and 1 treatment every other day) were responders. This study makes reference to the response rate for the sham group in the Sand et al study (13%). Using the 62% and 13% values in a chi-squared sample size calculation one finds that the treatment group for the proposed study should include 16 subjects.
- From a similar, ongoing study in which Elidah is also the Investigator (WIRB-20162650), to date, 71% of subjects are responders. Conservatively estimating the control responder rate at 15% (about the average rate reported in the AHRQ meta-analysis for the control groups in studies using vaginal EMS, Table F97), using a chi-squared sample size calculation one finds that the treatment group for the proposed study needs to enroll 12 subjects.

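### The responder endpoint is scored on only the first 5 and last 5 log entries, although more days are collected; the short windows create chance responders and cost power, not type I error.

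*Combined protocol and SAP*

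**What the plan says.** Section 9.5 defines the primary efficacy endpoint for each adherent woman: "The percent reduction in SUI episodes is then calculated by subtracting the final week average from the baseline average", and the difference is divided by the baseline average. A fall of at least 50% makes her a responder. The same section says that the baseline and 12th weeks mean the first 5 and last 5 log entries, because some entries will be omitted. Responders are compared by a one-tailed Fisher exact test at p≤0.025. No second assessment is required to confirm a response.

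More days than these are collected. Section 5.4 has a 7-day baseline log, and section 5.3 says "Subjects are required to maintain a Daily Log throughout the study", that is, from the baseline week through week 12. Table 5-1 prescribes one session per week throughout weeks 10 to 12.

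The baseline log also decides entry. Section 4.1 asks for a "self-reported typical number of accidents of 1 per 24 hours or more", to be verified against the log. Section 5.4 says that "If the 7 day baseline shows that the subject does not qualify based on urinary stress incontinence episodes", she is disqualified and no device is sent. That sentence gives no numeric cut-off.

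**The concern.** At about one episode per day, 5 days hold about 5 episodes. A count of that size can halve by chance, and a single halving settles the woman's outcome. A woman who logged 5 episodes in 5 baseline days responds with 2 or fewer in the last 5.

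Chance responders dilute the comparison. In the sham arm they raise a rate that the sizing in section 9.1 sets at 13-15%, and the difference that the Fisher test has to detect gets smaller. With 40 and 20 women there is little power to spare. Readings of the responder rate within one arm also become unsafe, because part of it is noise.

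**Working it through.** **The plan's own figures.** Section 9.1 states: "Each of these calculations target 80% power and assume an alpha of 2.5%, a 2:1 treatment to control randomization ratio, and a single-tailed test". With unpooled variance, n(treatment) = (1.960 + 0.842)² × [p₁(1−p₁) + 2p₂(1−p₂)] / (p₁−p₂)², where the squared term is 7.849.
- 48% v 13%: 7.849 × (0.2496 + 0.2262) / 0.1225 = 30.5, so 31.
- 62% v 13%: 7.849 × (0.2356 + 0.2262) / 0.2401 = 15.1, so 16.
- 71% v 15%: 7.849 × (0.2059 + 0.2550) / 0.3136 = 11.5, so 12.

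These match the plan. Its worked example, 24/40 v 5/20, gives a one-tailed Fisher p of 0.0105, also as stated. Exact Fisher power at 40/20 is 73.5% for 48% v 13% and 64.1% for 60% v 25%.

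**A closed-form illustration.** At a constant true rate of 1/day with Poisson counts, the last 5 days hold a Poisson(5) count. P(≤2) = e⁻⁵(1 + 5 + 12.5) = 12.5%. This holds the baseline at 5, so it contains no selection effect.

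**Women with one fixed true rate and no change.** Assumptions: independent Poisson days, and entry if the 7-day mean is between 1 and 5 per day (an assumed cut-off). The probability that the final mean is at most half the baseline mean, by exact summation:

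| True rate/day | 5 v 5 | 7 v 7 | 7 v 14 |
|---|---|---|---|
| 1 | 26.8% | 20.6% | 13.1% |
| 1.5 | 13.5% | 8.7% | 3.9% |
| 2 | 8.5% | 4.9% | 1.8% |
| 3 | 4.1% | 1.8% | 0.4% |
| 4 | 1.5% | 0.4% | 0.0% |

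**A mixed population, no change.** Assumptions: gamma true rates (shape 3), entry on at least 7 episodes in 7 days, and daily variance m + d·m² with d = 0 (Poisson), 0.5 (moderate) or 1 (strong). By simulation, across means of 1.5-2/day and d from 0 to 1:
- 5 v 5: about 11-29%
- 7 v 7: about 7-24%
- 7 v 14: about 4-18%

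At a mean of 3/day, 5 v 5 gives about 7-22%.

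**How much comes from re-using the qualifying week.** Give the same selected women an independent baseline week, still 5 v 5:
- mean 1.5/day, Poisson: 14.0% becomes 11.2%
- mean 2/day, Poisson: 10.7% becomes 9.0%
- worst case: 29.0% becomes 23.5%

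The differences are 2.8, 1.7 and 5.5 points. At fixed rates, selection matters near the entry floor (18.6% without it, 26.8% with it, at 1/day) and hardly at all at 2/day (8.4% against 8.5%). Window length accounts for most of the rest.

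**Type I error.** With a common responder rate in both arms, the rejection probability of the Fisher test at 40/20 never exceeds 0.0131.

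**Power at 40/20.** Assumptions: mean rate 1.8/day, median true reductions of 55% active and 15% sham, spread between women of log SD 0.4, one-tailed Fisher at 0.025.

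| Days | 5 v 5 | 7 v 7 | 7 v 14 |
|---|---|---|---|
| Poisson | 69% | 77% | 85% |
| Moderate overdispersion | 52% | 64% | 75% |

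The active rate barely moves (about 62-65%). The gain comes from a lower sham rate, for example 25% falling to 20% with Poisson days. Half of the Poisson gain (8 of 16 points) and about half of the other (12 of 23) comes simply from using 7 days rather than 5. With a shared week effect (log SD 0.3), 7 v 14 still gains 12-13 points over 7 v 7.

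**If benefit is still growing.** With the active week-11 reduction 5 points below week 12, the gain of 7 v 14 over 7 v 7 falls to about 2 to 3 points (other ways of modelling the lag give 1 to 6). With 10 points, 7 v 14 loses about 5 to 8 points against 7 v 7 and is roughly level to +5 against 5 v 5.

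**The case against.** The strongest reply is that the comparison stays valid. Both arms are randomised and the women are blinded, so chance response falls on both. A reader might infer that noise could produce a false positive; the Fisher bound of 0.0131 rules that out. The plan also expects control response: the first sizing scenario takes women who "were responders compared to 13% of subjects in a control (sham) group", the second repeats the 13%, the third uses 15%, and the worked example uses 25%. Sham rates observed in other studies already contain some chance responders. All of this stands, and it makes the point a refinement of power.

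Other stronger readings also fail.
- A reader might blame the double use of the qualifying week. It contributes only about 1 to 5 points over a mixed population, and lengthening the windows leaves it in place.
- A reader might suppose that only the sham arm is affected, because a woman who truly halves her rate is bound to count. She is not. At 1.5/day with 5 v 5 Poisson days, a true 50% cut is scored a response 59.5% of the time.
- A reader might take 11-29% as the trial's own figure. The documents give no daily variance, no expected episode rate and no numeric log cut-off. At 3-4/day, which section 4.2 still admits, the Poisson figure is 1.5-4.1%. At 1/day with daily variance up to three times the mean it can reach 47%.
- A reader might infer that section 5.4 drops days of menses or illness in week 12. It does not. It tells the woman to extend treatment by at least 5 days, which suits a last-5 window, whereas a last-14 window can reach back into those days.

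Two practical objections also stand. Table 5-1 marks the week 1-11 logs for compliance rather than endpoint analysis, and section 5.3 expects gaps between baseline and week 12. A longer window therefore needs a missing-entry rule.

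**Conclusion.** The point holds as an avoidable loss of power. Section 9.5 discards logged days at both ends, and under the stated assumptions more than doubles chance response at the lower end of the range (11% against 4%) compared with a 7 v 14 rule. The power cost against 7 v 14 is about 16 points with Poisson days (69% to 85%) and 23 with moderate overdispersion (52% to 75%). Moving to 7 v 7 recovers about half of this and does not depend on the week-11 effect. The 14-day final window adds the rest only if the week-11 benefit is close to that of week 12. The sizes rest on assumed episode rates, dispersion, entry cut-off and treatment effects; the direction of the noise reduction does not depend on a particular choice among those examined. The plan should be changed, but the primary test is not invalid as it stands.

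**What to change.** In section 9.5:
- Define baseline as the mean of all logged baseline days, up to 7.
- Define the final value as the mean of the last 14 logged days within weeks 10-12 or the week-13 extension. If fewer than 14 are logged, use all that are available.
- Require at least 5 entries in each window.
- State, before unblinding, how days noted as menses or illness are handled in the analysis.
- Keep the ≥50% rule and the Fisher test, and report the week-12-only version as a sensitivity analysis.

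Align the Table 5-1 legend so that the added log weeks count as endpoint data.

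Cost: no new data collection, no more subjects and no change of test. It does redefine the primary endpoint, and section 9.6 says that FDA gave input on the outcome measures, so the wording should be settled with the agency before unblinding. The endpoint would then describe about weeks 11-12 rather than week 12, with the loss shown above if benefit is still rising. Re-use of the qualifying week remains.

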These three analyses suggest a treatment group in the range of 12-31 subjects. Taking a conservative approach, Elidah will aim to enroll 40 subjects in the treatment group and 20 subjects in the control group. At that level of enrollment, responder rates of 60% and 25% would give p=0.01. Anticipating that some subjects will drop out throughout the study, a total of 70-80 subjects will be identified for participation. See 9.4 regarding interim analysis and stopping rules.

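### The one-tailed Fisher test in 9.5 is valid but conservative at 40/20; a final Boschloo exact test would gain power on the same subjects, if its cut-off allows for the interim looks and the actual arm sizes

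*Combined protocol and SAP*

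**What the plan says.** Section 9.5 classes each adherent subject as a responder if SUI episodes per day fall by at least 50%. It then states: "The number of responders from each group is then compared using a one-tailed Fisher's exact test for groups of unequal size", with success at p≤0.025. Its worked example is 24/40 v 5/20, with p=0.01.

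Section 9.1 says the sample-size calculations "target 80% power and assume an alpha of 2.5%, a 2:1 treatment to control randomization ratio, and a single-tailed test". They use a chi-squared method, not Fisher's test, for three pairs of responder rates: 48% v 13%, 62% v 13% and 71% v 15%. These give treatment arms of 31, 16 and 12. The plan then goes higher: "Elidah will aim to enroll 40 subjects in the treatment group and 20 subjects in the control group".

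Section 9.4 adds efficacy looks after 30 and 45 subjects, with a p<0.0013 boundary on the p-value for the primary efficacy outcome. It does not state the arm split at each look. The documents give neither the true error rate of Fisher's test at 40/20 nor its power there.

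**The concern.** Fisher's test conditions on the total number of responders. With 40 and 20 subjects, few p-values are attainable for a given total, so the true error rate can fall well below the nominal 2.5%. The unused error is lost power. The sizing in 9.1 would not show this, because it rests on a normal approximation and not on the test that decides the trial.

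At stake is the chance that a truly effective device fails the primary test. An exact test that conditions on less can recover some of that power without more subjects, visits or data.

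**Working it through.** **Inputs.** One-sided alpha 0.025, 80% power and 2:1 allocation (9.1); final arms 40/20 (9.1); Fisher p≤0.025 (9.5); looks at 30 and 45 subjects with p<0.0013 (9.4). Assumption: the looks split 20/10 and 30/15.

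**The plan's own figures.** The unpooled normal formula is n_T = (1.960+0.842)² × [p_T(1−p_T) + 2p_C(1−p_C)] / (p_T−p_C)².

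- 48% v 13%: 7.849 × 0.4758 / 0.1225 = 30.49, so 31.
- 62% v 13%: 7.849 × 0.4618 / 0.2401 = 15.10, so 16.
- 71% v 15%: 7.849 × 0.4609 / 0.3136 = 11.54, so 12.

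All three match 9.1. One-tailed Fisher for 24/40 v 5/20 gives p=0.01047, which matches the stated 0.01.

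**Error of Fisher's test at 40/20.** For each of the 41×21 tables (x, y), the Fisher p-value is the hypergeometric probability P(X≥x | X+Y=x+y). With R the set of tables where p≤0.025, the error at a common responder rate π is the sum over R of C(40,x) C(20,y) π^(x+y) (1−π)^(60−x−y).

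- Largest value: 1.31%, at π of about 0.35.
- At π = 13%: 0.49%. At 15%: 0.70%. At 25%: 1.26%.
- With both p<0.0013 looks included, the maximum is 1.32%.

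**Boschloo at 40/20.** Boschloo's test orders tables by the Fisher p-value but takes its error from the two binomial distributions, at the worst common rate. Its 0.025 region is Fisher p≤0.0405, with maximum error 2.49%. The next attainable step, 0.0408, would give 2.74%. Every table that Fisher rejects is also rejected. With 5/20 control responders, Fisher needs 23/40 active responders (22/40 gives p=0.0258). Boschloo needs 21/40 (Fisher p=0.0386, Boschloo p=0.0226).

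**Power at 40/20, single look** (the same sum, with separate rates for the arms):

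| Active v control | Role in the plan | Fisher | Boschloo | Gain (points) |
|---|---|---|---|---|
| 48% v 13% | planning | 73.5% | 80.3% | 6.8 |
| 62% v 13% | planning | 95.5% | 97.8% | 2.2 |
| 71% v 15% | planning | 98.6% | 99.4% | 0.8 |
| 60% v 25% | illustration only | 64.1% | 74.9% | 10.8 |

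(Gains are taken before rounding.) With the looks included, the gains at 48% v 13% and 60% v 25% change by no more than about 0.1 point.

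**Overall error with both looks**, by exact convolution over 20/10, 30/15 and 40/20:

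| Test at looks | Final region | Overall error |
|---|---|---|
| Fisher p<0.0013 | Boschloo, full (Fisher p≤0.0405) | 2.495% |
| Boschloo p<0.0013 | Boschloo, full | 2.53% |
| Fisher p<0.0013 | one step lower (Fisher p≤0.0396) | 2.38% |

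The trimmed region drops a single table, 23/40 v 6/20. Its power is 80.1% at 48% v 13% and 72.9% at 60% v 25%. Moving the first look's split between 18/12 and 21/9 leaves the first row at 2.49–2.50%.

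**Other arm sizes.** From 36/18 to 44/22, the gain at 48% v 13% is mostly 7 to 10 points: 9.8 at 36/18, 8.9 at 38/19, 8.2 at 41/19 and 7.3 at 44/22. It falls to 6.0 at 39/21 and 5.4 at 43/21. Boschloo's power at 48% v 13% is 75.9% at 36/18, 77.8% at 42/18 and 79.1% at 41/19. At 36/18, Fisher looks followed by the full Boschloo region give an overall error of 2.502%.

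**The case against.** The strongest reply is that nothing in 9.5 is wrong. The plan pre-specifies a valid exact test, treats 0.025 as a ceiling and respects it, and its worked example reproduces. Fisher's test also holds its level at any arm sizes without recalculation. All of this stands. A reader might infer that the plan misstates its alpha or uses an invalid test; the documents do not support that.

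Four other stronger readings also fail.

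- **A gain of 7 to 11 points across the plan's scenarios.** The larger figure comes from 60% v 25%, which 9.1 and 9.5 use only to illustrate a p-value. In two of the three planning scenarios Fisher's power already exceeds 95%, and the gain is 2.2 and 0.8 points.
- **Boschloo secures the 80% target.** At 40/20 it clears the target by 0.3 points. The primary analysis takes adherent subjects only (5.5, 9.5) and assignment is in blocks of nine (9.2), so exactly 40/20 is not assured. Somewhat smaller or less balanced arms fall short.
- **Boschloo stays within 2.5% whatever is done at the looks.** Section 9.4 ties its boundary to the primary outcome's p-value. If Boschloo is used throughout, overall error is 2.53%; even with Fisher looks there is almost no margin.
- **The same swap suits the secondary measures.** For pad weight, 9.5 says "the groups will be compared using the Fisher's exact test in a similar manner to the analysis of the primary outcome measure". But size and power were not worked out for the secondary measures under the Hochberg procedure, and pad use excludes women who used no pad at baseline, so its arm sizes are unknown.

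The reply does not remove the central point. The plan sets an 80% target, and its decision test gives 73.5% in its hardest scenario at the planned size.

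**Conclusion.** The point holds as a recommended efficiency gain. At 40/20, Fisher's test uses at most about 1.3% of the permitted 2.5%, and only 0.5–0.7% at common rates of 13–15%. A final Boschloo test adds 0.8 to 6.8 points of power across the plan's three planning scenarios. The benefit is largest where success is in doubt, and it survives trimming the cut-off to leave a margin for the interim looks.

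The 40/20 figures rest on exactly 40 and 20 analysed subjects, and the overall error figures also on looks at 20/10 and 30/15. The direction of the gain held at every nearby size tried; reaching 80% did not.

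**What to change.** Before any unblinded look:

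- In 9.5, make the final primary test a one-sided Boschloo exact test, and report the Fisher p-value beside it.
- In 9.4, state that the p<0.0013 looks use Fisher's one-tailed p-value.
- In 9.5, state that the final cut-off is set from the arm sizes actually analysed, before group results are seen, so that overall one-sided error including both looks is at most 2.5%. At 40/20, with the assumed splits, Fisher p≤0.0396 meets this with a margin (2.38%).
- Leave the tests for the secondary measures as they are.

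No subjects, visits or data are added. The costs are a test less familiar to readers, a cut-off that must be recalculated for the actual arms, and a protocol amendment that needs IRB review and approval (11.1).

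### Does leaving the sidedness of the three secondary tests unstated, at a Hochberg total of 0.05, make their error control unsound?

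*Combined protocol and SAP*

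**What the plan says.** For the primary endpoint, section 9.5 states the tail and the level. Responder counts are "compared using a one-tailed Fisher's exact test for groups of unequal size", with success at p≤0.025. Section 9.1 agrees: "Each of these calculations target 80% power and assume an alpha of 2.5%, a 2:1 treatment to control randomization ratio, and a single-tailed test".

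For the secondary endpoints, section 9.5 says that "three tests are prospectively defined with the intent of using the results to support future product labeling and marketing". Error across the three is handled by Hochberg's method, which "with a total alpha of 0.05 will be used to address multiple endpoint related multiplicity problems", and the order of testing is fixed: "These secondary outcome measures are only intended to be analyzed if the primary efficacy endpoint is met".

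The three tests are described unevenly:
- **24h pad weight:** responders are compared by Fisher's "exact test in a similar manner to the analysis of the primary outcome measure".
- **I-QoL:** "Treatment and control groups will be compared using the Fisher's exact test", with no tail given.
- **Pad use:** "As with the 24h pad weight test, reduction in pad usage will be assessed", with a 50% criterion but no test named.

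Nothing in the document says whether the 0.05, or any of the three tests, is one- or two-tailed.

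**The concern.** The plan fixes both tail and level for the primary, and only a level for the secondaries. The pointers back to the primary make a one-tailed test the natural reading for pad weight and, through pad weight, for pad use. One-tailed testing at a total of 0.05 would then give claims meant for labelling and marketing a nominal threshold twice that of the primary.

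The choice could also be made late. Section 9.3 says that blinding is broken at group analysis, so an analyst could in principle choose the tail with the results in view, and the same data could yield different claims. At stake are the secondary claims, not the primary conclusion.

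**Working it through.** **Inputs from the plan.** 40 active and 20 control subjects (9.1); primary one-tailed Fisher at 0.025 (9.5); three secondaries, Hochberg total 0.05, tested only if the primary is met (9.5).

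**Assumptions, not in the plan.** Responder rates on the secondaries, correlation between endpoints, and all 40 and 20 subjects analysed for each endpoint. Pad use will have fewer, since subjects who use no pads at baseline are excluded.

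**1. The plan's own example.** For 24/40 against 5/20, one-tailed Fisher gives p=0.0105, which reproduces the stated 0.01. The two-tailed value is 0.0142. It also rounds to 0.01, so the example does not itself reveal the tail; the text does.

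**2. Hochberg steps.** With three tests and total α, the largest p-value is compared with α, the middle one with α/2 and the smallest with α/3.
- α = 0.05: 0.05, 0.025, 0.0167
- α = 0.025: 0.025, 0.0125, 0.0083

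The ratio is 2 at every step. A two-tailed 0.05 puts 0.05/2 = 0.025 in the favourable direction, the same nominal level as the primary.

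**3. Where the tail changes a result.** Take 5/20 control responders and the most lenient Hochberg step, which applies when all three endpoints give the same result.

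| Active responders | One-tailed p | Two-tailed p |
|---|---|---|
| 21/40 | 0.0386 | 0.0556 |
| 22/40 | 0.0258 | 0.0322 |
| 23/40 | 0.0167 | 0.0274 |

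The smallest passing count is 21 at one-tailed 0.05, 22 at two-tailed 0.05 and 23 at one-tailed 0.025. The two readings that the text allows, both at 0.05, differ by one responder here.

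**4. False claims.** Three binary endpoints were simulated with no true effect, common responder rates of 15-65% and latent correlations of 0, 0.5 and 0.8. The chance of at least one false claim of benefit, before requiring the primary to be met, was:
- one-tailed 0.05: 0.95-2.62%
- two-tailed 0.05, favourable direction: 0.43-1.92%
- one-tailed 0.025: 0.36-1.21%

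These rates fall well below nominal because Fisher's test is discrete. A single one-tailed test at 0.05 has an actual size of 1.97%, 2.24% and 2.73% at common rates of 15%, 25% and 50%. That single-test size also covers the case where two endpoints truly respond and are declared, so that the third, null endpoint is tested at the full 0.05. Over the all-null and one-null cases, the range at one-tailed 0.05 is about 0.9-2.7%.

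If the primary must also be met (assumed 60% against 25%, met in 64% of trials), the chance of meeting it and making a false secondary claim at one-tailed 0.05 is 1.4-2.2%, for null secondaries at 25-65%.

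**5. How often the two readings disagree when the effect is real.** Assume secondaries at 50% against 25%, the primary at 60% against 25%, and correlation 0 or 0.5. Among trials that meet the primary:
- at least one secondary is declared in 66-68% at one-tailed 0.05 and in 58-60% at two-tailed 0.05;
- the set of declared endpoints differs between these two readings in about 18-20%.

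A comparison of one-tailed 0.05 with one-tailed 0.025 gives a larger difference, 27-28%, but the plan sets no 0.025 level for the secondaries. That figure measures a rule the plan does not contain.

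**The case for a change.** The strongest case for a change is that multiplicity control is incomplete while the tail is open. Testing the primary first protects only the primary's error rate. Once it is met, the secondary family runs at its own level, and that is when claims are made. With 21/40 against 5/20 on all three endpoints, the data pass or fail on an unwritten choice. The remedy would be one sentence, and the convention that 0.05 means two-sided is a weak guide in a plan whose only fully specified between-group test is one-tailed.

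Most of this is true as description. The tail is unstated, it can alter a secondary claim, and writing it down would cost little. What does not follow is that the plan as written leads to an unsound analysis. A secondary family tested after the primary may carry a larger nominal level than the primary; nothing in the document forbids it, and matching the two is a convention. The doubling is nominal, since the realised error on the looser reading is at or about 2.5%.

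The room for a convenient choice is also limited. The pointers for pad weight and pad use lead back to the primary's test, which leaves only I-QoL without one. Responder counts by arm allow any reader to compute either p-value. Section 10.6 has people outside the original analysis audit the calculations and the statistical conclusions.

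**Conclusion.** No change is needed. The plan leaves a detail unwritten, and an analyst can fill it in either of two acceptable ways. Two-tailed 0.05 agrees with the primary's nominal level. One-tailed 0.05 follows the pointers in the text, leaves the primary's type I error alone, and gives a simulated family-wise false-claim rate of about 0.9-2.7%.

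The practical consequence is confined to secondary claims: a different set of endpoints in about 18-20% of trials that meet the primary, and at least one claim in 66-68% against 58-60%. These figures rest on assumed responder rates (50% against 25% for the secondaries, 60% against 25% for the primary), assumed correlations, and full groups of 40 and 20. The false-claim range depends on Fisher's test being used for all three endpoints, including pad use, where the test is implied rather than named.
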